4.10 Handling of missing and incomplete data

All reasonable efforts will be made to reduce the rate of missing data. Investigators will be trained about the importance of patient retention and full data capture. Also, any reasonable attempts should be made by the investigators to emphasize continued subject's participation for the full duration of the trial.

Patients who discontinue the treatment will not be withdrawn from the study by default, but will be asked to complete safety and efficacy observations as per the protocol, unless otherwise they withdraw their consent. Patients who discontinue study treatment and decide to remain in the study by following the schedule of assessments and continuing to adhere to protocol requirements are defined as "retrieved dropout" patients (section 11.1.1 provides details on the definition).

For the main analyses of the primary endpoints, missing data will be managed as follows:

- Missing data due to death, preventing the collection of the endpoint, will be imputed with an unfavourable value (see section 4.4.1).
- Missing data in extubated patient, preventing the collection of the endpoint (for Change in OI at Day 7 only), will be imputed with a favourable value (see section 4.4.1).
- Missing data due to treatment discontinuation or any other reason (whichever the reason) will be handled by means of Multiple Imputation (MI) approach as detailed in Section 7.1.1.

Sensitivity analysis of the primary endpoints can be based on different missingness assumptions (section 7.1.2.1)

In the descriptive summaries, the number of subjects with missing data will be presented under the "Missing" category. Missing values will be included in the denominator count when computing percentages. When continuous data will be summarized, only the non-missing values will be evaluated for computing summary statistics. Any exception will be declared.

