7.2.1.12 Incidence of transfer to long term acute care (LTAC) facility

Rules for derivation of Incidence of transfer to LTAC facility are reported in section 11.1.

The proportion of patients with transfer to LTAC facility by Day 28 and at hospital discharge will be compared by Fisher's exact test or Chi-square's test, depending on data distribution.

7.2.1.13 All-cause mortality by day 28 and by day 60

Rules for derivation of All-cause mortality by day 28 and by day 60 are reported in section 11.1.

The number and proportion of deaths within Day 28 and within Day 60 will be reported and compared by Fisher's exact test.

Freedom from death will also be analyzed and graphically represented as described in Section 4.1 following a time-to-event approach.

An additional analysis for time to death will be performed where study discontinuations for Adverse Event, Death, and Loss to follow-up will be considered as failure events.

7.2.1.14 Patients discharged by day 28

The number and proportion of patients discharged (alive) at Day 28 (as defined in section 11.1) will be reported and compared by Fisher's exact test.

7.2.1.15 Change from baseline to Day 3, 7 and 14 in plasma levels of IL-6, IL-8, PAI-1, Plasma TNFr-1, ICAM-1, RAGE

Value and change from baseline to Day 3, 7 and 14 in biomarkers plasma levels of IL-6, IL-8, PAI-1, Plasma TNFr-1, ICAM-1, RAGE will be analyzed by means of descriptive statistics as a continuous variable. Comparison between treatments will be performed by means of two-sample t-test and, if assumptions of normality is not confirmed, two-sample Mann-Whitney U test.

Boxplot for values and changes from baseline will also be graphically represented by treatment at each timepoint.

In the case parameters are reported with a result containing a qualifier (e.g.: "<2.5", ">3.4") the value will be analyzed by stripping out the qualifiers:

- if the value contains a qualifier "<" with a decimal place (<X.X), the value will be analyzed as: X.X;

Standard/Forms/Template				
Title		Statistical Analysis Plan Template		
Code		Version	Effective Date	Page
PPD		01	29 Aug 2022	51 of 78

- if the value contains a qualifier “>” with a decimal place (>X.X) the value will be analyzed as: X.X.

A listing on biomarkers results will be provided as well.

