Hospital stay up to Day 28 (days) [study day based on Date]	
Hospital stay up to Day 28 :
 
Date of discharge* – First IMP Intake date + 1.
 
If Date of discharge* is after Day 28 date, then Day 28 date will be used instead.
 
If Date of discharge* is missing and date of death\geq Day 28 date then date of Discharge = Day 28 date.
 
If Date of discharge* is missing and last available day \geq 26 then date of Discharge = Day 28 date.
 
Otherwise the endpoint is set as missing.
 
Day 28 date: Day 1 date + 27
 
*date of discharge is collected in End of Study form; in the case it is missing it is taken from Visit date in "Hospital Discharge".

Hospital-free days by Day 28 [study day based on Date]	
Hospital-free days by Day 28
 
If patient is alive at Day 28 (last available day \geq 26): Hospital-free days = 28 – Hospital stay up to Day 28
 
If patient dies within Day 28: Hospital-free days = 0
 
Otherwise, If subject is alive and followed for $<$ 26 days (last available day $<$ 26) the endpoint is set as missing.
 
Day 28= Day 1 date + 27

Standard/Forms/Template				
Title		Statistical Analysis Plan Template		
Code		Version	Effective Date	Page
PPD		01	29 Aug 2022	66 of 78

Parameter	Calculation
Patients discharged (alive) by Day 28 [study day based on Date]	
A patient is considered discharged alive by Day 28:
 
 - if patient is discharged* before Day 28 (included) (regardless the vital status after discharge). 
Otherwise, a patient is considered not alive and discharged by Day 28:
 
 - if patient dies and date of discharge* is missing, OR - if patient is not discharged* before Day 28 (included) (day of discharge >28) OR - if date of discharge is missing, but subject is in study long enough (last available day ≥ 26) OR - Discharge date=Death date (assumptions: patient died in the hospital) 
Otherwise, if the date of discharge is missing and subject is alive and followed for <26 days (last available date<26) the endpoint is set as missing.
 
Day 28: Day 1 + 27
 
*date of discharge is collected in EOS; in the case it is missing it is taken from Visit date in "Hospital Discharge".

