Incidence of tracheostomies by day 28 and hospital discharge [study visit]	
Performance of tracheostomy (Y/N) and date of tracheostomy is collected in "Other Clinical Event" CRF Form.
 
Incidence of tracheostomy by Day 28 :
 
event = "Y" if date of tracheostomy is performed between date of 1st IMP intake and Day 28 visit date.
 
otherwise event = "N" if ((date of tracheostomy is missing or < date 1st IMP intake) and day 28 visit is present) or (date of tracheostomy > day 28 visit)
 
otherwise event is missing if day 28 visit is missing.
 
Incidence of tracheostomy by hospital discharge:
 
event = "Y" if date of tracheostomy is performed between date of 1st IMP intake and date of Hospital Discharge* (included). In the case the discharge date is missing (but the date of tracheostomy is not missing), it is assumed that the patient is at the hospital (as the tracheostomy can only be performed at the hospital) therefore the event will be = "Y".
 
otherwise event = "N" if ((date of tracheostomy is missing or < date 1st IMP intake) and date hospital discharge* is present) or (date of tracheostomy > hospital discharge*)
 
otherwise event is missing .
 
note: if date hospital discharge is missing and patient died then date hospital discharge* = date death.
 
*date of discharge is collected in EOS; in the case it is missing it is taken from Visit date in "Hospital Discharge".

Standard/Forms/Template				
Title		Statistical Analysis Plan Template		
Code		Version	Effective Date	Page
PPD		01	29 Aug 2022	68 of 78

Parameter	Calculation

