Incidence of LTAC facility by day 28 and hospital discharge [study visit]	
Performance of LTAC facility (Y/N) and date of LTAC facility is collected in "Other Clinical Event" CRF Form.
 
Incidence of LTAC facility by Day 28 :
 
event = "Y" if date of LTAC facility is performed between date of 1st IMP intake and Day 28 visit date.
 
otherwise event = "N" if ((date of LTAC facility is missing or < date 1st IMP intake) and day 28 visit is present) or (date of LTAC facility > day 28 visit)
 
otherwise event is missing if day 28 visit is missing
 
Incidence of LTAC facility by hospital discharge:
 
event = "Y" if date of LTAC facility is performed between date of 1st IMP intake and Date of Hospital Discharge* (included). In the case the discharge date is missing (but the date of LTAC facility is not missing), it is assumed that the patient is at the hospital therefore the event will be = "Y".
 
otherwise event = "N" if ((date of LTAC facility is missing or < date 1st IMP intake) and date hospital discharge* is present) or (date of LTAC facility > hospital discharge*)
 
otherwise event is missing if hospital discharge is missing
 
note: if date hospital discharge* is missing and patient died then date hospital discharge* = date death
 
*date of discharge is collected in EOS; in the case it is missing it is taken from Visit date in "Hospital Discharge".

Standard/Forms/Template				
Title		Statistical Analysis Plan Template		
Code		Version	Effective Date	Page
PPD		01	29 Aug 2022	69 of 78

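### An in-hospital death without tracheostomy or LTAC transfer is a non-event by hospital discharge but missing by Day 28, so mortality can lower the by-discharge incidence and the two horizons disagree

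*SAP*

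**What the plan says.** Both endpoints are secondary and have two horizons, Day 28 and hospital discharge. The derivations are in SAP section 11.1.1, Table 3.

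**By hospital discharge.** The LTAC row carries the note "note: if date hospital discharge* is missing and patient died then date hospital discharge* = date death". The tracheostomy row has the same note: "note: if date hospital discharge is missing and patient died then date hospital discharge* = date death". A patient is 'N' when there is no event date on or after the first dose "and date hospital discharge* is present) or (date of LTAC facility > hospital discharge" date; the tracheostomy row reads "and date hospital discharge* is present) or (date of tracheostomy > hospital discharge" date. Neither row checks vital status.

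**By Day 28.** Without an event, 'N' requires a Day 28 visit; failing that, "otherwise event is missing if day 28 visit is missing".

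**Analysis.** SAP 7.2.1.12 states: "The proportion of patients with transfer to LTAC facility by Day 28 and at hospital discharge will be compared by" Fisher's exact or chi-squared test. SAP 7.2.1.11 does the same for tracheostomy. Under SAP 7.2.1 the level is 0.05 two-sided without multiplicity correction, and under SAP 3.3 p-values are descriptive only. On percentages, SAP 4.10 says: "Missing values will be included in the denominator count when computing percentages".

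**Death elsewhere.** For hospital-free days, "If patient dies within Day 28: Hospital-free days = 0". For discharge alive by Day 28, a discharge date equal to the death date is read as an in-hospital death and kept apart from live discharge. Mortality is reported at Day 28 and Day 60 (SAP 7.2.1.13).

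**The concern.** The by-discharge 'N' group pools two opposite outcomes: patients who left hospital alive without the event, and patients who died there without it. None of the planned outputs described in the SAP shows how many of the 'N' patients died. A reader who takes a lower incidence as good news could be reading mortality instead. A treatment that kept alive patients who then needed prolonged care could look unfavourable on LTAC.

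The second problem is consistency. The same early death counts as a non-event in one tested proportion and as missing in the other. A difference between the Day 28 and by-discharge results could then come from the scoring rule alone.

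**Working it through.** The plan gives no figure for these endpoints, so there is none to reproduce.

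**Inputs**
- Scoring rules: SAP 11.1.1, Table 3.
- Arm size: about 66 enrolled 1:1 (SAP 3.3), so about 33 per arm.
- Mortality of 27% and 45%: protocol 2.6.2.3, quoted there as disease-associated mortality by severity. Used here only as an illustrative pair.
- Event rates among survivors and before death: not in the documents, so assumed.

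**Step 1. Apply the rules to single patients** (taking it that a patient who has died has no Day 28 visit record)

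| Patient | By discharge | By Day 28 |
|---|---|---|
| Home on Day 20, no event, Day 28 visit done | N | N |
| Dies in hospital Day 10, no event, discharge date blank | N | missing |
| Dies in hospital Day 10, no event, discharge date entered as death date | N | missing |
| Dies in hospital after the Day 28 visit, no event | N | N |
| Event Day 8, dies Day 10 | Y | depends on how the blank visit date is read |
| Alive, Day 28 visit done, no discharge date, no event | missing | N |

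**Step 2. LTAC.** The protocol describes LTAC patients as coming directly from intensive care, so a patient who dies in the index hospital has normally not been transferred. With LTAC risk r among survivors, equal in both arms, and in-hospital mortality m:

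incidence = r(1 − m); difference between arms = r × (mortality difference).

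At r = 0.25: 0.25 × 0.73 = 18.25% against 0.25 × 0.55 = 13.75%, a 4.5-point advantage for the arm with more deaths. Shift in points for other values:

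| Mortality gap | r = 10% | r = 25% | r = 40% |
|---|---|---|---|
| 5 points | 0.5 | 1.25 | 2.0 |
| 10 points | 1.0 | 2.5 | 4.0 |
| 18 points | 1.8 | 4.5 | 7.2 |

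At r = 25% this is 33 × 0.0125 = 0.4, 33 × 0.025 = 0.8 and 33 × 0.045 = 1.5 patients per arm.

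**Step 3. Tracheostomy.** Procedures before death still count 'Y'. With rate s in survivors and q in patients who die:

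incidence = (1 − m)s + mq; difference (higher-mortality arm minus lower) = (mortality difference) × (q − s).

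At s = 30% and mortality 27% against 45%:
- q = 0: 21.9% against 16.5%, difference −5.4 points
- q = 15%: 25.95% against 23.25%, −2.7 points
- q = 30%: 30% against 30%, 0
- q = 45%: 34.05% against 36.75%, +2.7 points

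The sign depends on q relative to s.

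**Step 4. The two horizons side by side.** Take 33 per arm, 9 against 15 deaths, and the event in one third of survivors and in no patient who dies: 8 of 24 and 6 of 18. Suppose all events and deaths fall before the Day 28 visit.
- By discharge: 8/33 = 24.2% against 6/33 = 18.2%, Fisher p = 0.76.
- By Day 28, if the test uses only 'Y' and 'N': 8/24 = 33.3% against 6/18 = 33.3%, no difference.
- By Day 28, descriptive percentage with missing in the denominator: 8/33 and 6/33 again.
- Event or death: (8 + 9)/33 = 51.5% against (6 + 15)/33 = 63.6%, p = 0.46.

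The same patients give a 6-point difference in one test and none in the other.

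**The case against.** **The rule is defensible as an incidence.** A patient who died in hospital without a tracheostomy did not have one, and follow-up for it is complete. Incidence with death as a competing event is a recognised summary. This stands, provided the choice is declared and the result is read together with deaths. The SAP does neither for these endpoints.

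**Death is reported elsewhere.** Day 28 and Day 60 mortality, the death tables and discharge alive by Day 28 all inform the reader. That helps, but none is at the by-discharge horizon and none splits the 'N' group.

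**The SAP is not simply contradicting itself.** A reader might infer this because ventilator-free and hospital-free days score death as 0. Those are failure-free-day scores, where the zero belongs to the definition. The closer comparators are the binary ECMO and vasoactive endpoints, which also do not count death as an event: a death without the event is 'N' from last available day 12 and missing before it. This objection stands.

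**More deaths need not look better.** A reader might infer that the arm with more deaths will look better on both endpoints. The documents do not support that: for tracheostomy, Step 3 shows the advantage vanishing or reversing. Nor do they state that fewer events is better, and the tests are two-sided.

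**The size is small.** The 18-point gap is constructed from a severity range and is not a contrast between randomised arms. The event-or-death ordering in Step 4 follows from the assumed death gap, so it is no independent evidence. At 25% LTAC risk even the 18-point gap moves about 1.5 patients per arm.

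**Conclusion.** The scoring is as described for both endpoints, and no other section corrects it. Two conclusions follow.

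1. By discharge, an in-hospital death without the event cannot be told apart from a live discharge without it. For LTAC, higher mortality then lowers the incidence almost by construction, by r times the mortality difference. At the assumed 25% that is about 1.3, 2.5 and 4.5 points for gaps of 5, 10 and 18 points. For tracheostomy the direction is conditional on how often patients who die had the procedure first.
2. A death before the Day 28 visit without the event is missing at Day 28 but 'N' by discharge. The effect falls on the tests, because the descriptive percentages keep missing values in the denominator.

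These sizes rest on an equal LTAC risk among survivors in both arms and on no transfers before in-hospital death. The documents give no LTAC rate. The point is minor: the endpoints are secondary, there are no formal hypotheses, and a bias of this size alone is unlikely to reach significance with about 33 per arm. It is still worth correcting, because the correction is cheap and stops death being read as a good outcome.

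**What to change.** In both Table 3 rows, replace the note and the Day 28 missing rule with one classification used at both horizons:
- event, tested first so that an event before death counts;
- died in hospital without the event, including records where the discharge date equals the death date;
- alive without the event.

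Keep missing for patients whose status is truly unknown, and state where a death after live discharge but before Day 28 belongs.

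Tabulate the three categories by arm beside the Fisher or chi-squared comparison. Treat deaths the same way in the test at both horizons; keeping them in the denominator as labelled non-events is the simplest choice and fits an incidence endpoint. State that the event percentage is to be read together with the deaths.

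Deleting the note alone is not enough. Deaths with a blank discharge date would become missing, and deaths with discharge date equal to death date would stay 'N'.

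Event or in-hospital death may be added as a supportive analysis with its components shown. It need not replace the incidence endpoint, because death would dominate it: in the Step 2 illustration, 27/45.25 = 60% and 45/58.75 = 77% of the composite.

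**Cost:** SAP wording, two re-derived variables and slightly larger tables. All dates are already collected. If the database is already locked, document the change in the clinical study report.

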14.4.5. Acute lung Injury Score

Component	0	1	2	3	4
Chest X-ray (Alveolar infiltrates)	No	1 quadrant	2 quadrants	3 quadrants	4 quadrants
Hypoxaemia ($\text{PaO}_2/\text{FiO}_2$, mmHg)	≥ 300	225–299	175–224	100–174	≤ 100
PEEP (PEEP-setting, cmH_2O)	≤ 5	6–8	9–11	12–14	≥ 15
Compliance (Static, $\text{mL}/\text{cmH}_2\text{O}$)	≥ 80	60–79	40–59	30–39	≤ 29

From: Murray JF et al. An expanded definition of the adult respiratory distress syndrome. Am Rev Respir Dis 1988;138:720-3

The final score is obtained by dividing the collective score by the number of components that were used.

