14.4.11 Ventilator-free days (VFDs)

VFDs is a well-known endpoint, often used in adult and pediatric ARDS trials; 28-day is the most common time frame for VFDs in ARDS.

VFDs at 28 days is defined as follows³⁶:

- VFDs = 0 if the patients die within 28 days
- VFDs = 28 – x if successfully liberated from ventilation x days after initiation
- VFDs = 0 if the patients are mechanically ventilated for >28 days

14.5. APPENDIX 14.5 - CLINICAL TRIALS SUBJECT TO TRANSITION FROM EUROPEAN DIRECTIVE 2001/20/EC TO CLINICAL TRIAL REGULATION EU NO 536/2014

REP0122 (EudraCT 2022-001612-25) constitutes a Consolidated Protocol and the minor differences between the nationally authorized trials is summarized in the following table:

EU Member State	Minor Difference of trial conduct
Germany	Chest imaging has to be performed as per local clinical practice/needs.

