7.2.1.2 Acute lung injury score

Rules for derivation of Acute lung injury score are reported in section 11.1.

Value and change from baseline in Acute lung injury score will be analyzed at Day 2, Day 3, Day 7, Day 14 (if still intubated) timepoints by means of descriptive statistics as a continuous variable. Comparison between treatments will be performed by means of two-sample t-test and, if assumption of normality is not confirmed, two-sample Mann-Whitney U test.

Acute lung injury score classes (as defined in section 11.1.1.) will also be summarized as a categorical variable: number and percentage of patients in each class for each timepoint will be presented and a shift table will be provided.

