
Standard/Forms/Template			
Title	Statistical Analysis Plan Template		
Code	Version	Effective Date	Page
PPD	01	29 Aug 2022	71 of 78

Acute lung injury score [by visit and date/time]	
As per study protocol, acute lung injury score is a composite value of $\text{PaO}_2/\text{FiO}_2$ ratio, PEEP, lung compliance (plateau airway pressure minus PEEP/TV) and extent of pulmonary infiltrates.
 
  
 		Value	
   
 1. Chest X-ray (Number of quadrants with alveolar infiltrates)			
 
 0		0	
 
 1 quadrant		1	
 
 2 quadrants		2	
 
 3 quadrants		3	
 
 4 quadrants		4	
 
 2. Hypoxemia score ($\text{PaO}_2/\text{FiO}_2$ mmHg)			
 
 $\text{PaO}_2/\text{FiO}_2$	$\geq 300$	0	
 
 $\text{PaO}_2/\text{FiO}_2$	225-<300	1	
 
 $\text{PaO}_2/\text{FiO}_2$	175-<225	2	
 
 $\text{PaO}_2/\text{FiO}_2$	100-<175	3	
 
 $\text{PaO}_2/\text{FiO}_2$	<100	4	
 
 3. PEEP score (cmH₂O)			
 
 PEEP	≤ 5 cmH₂O	0	
 
 PEEP	6-8.99 cmH₂O	1	
 
 PEEP	9-11.99 cmH₂O	2	
 
 PEEP	12-14.99 cmH₂O	3	
 
 PEEP	≥ 15 cmH₂O	4	
 
 4. Compliance (ml/cmH₂O)			
 
 Compliance	≥ 80 ml/cmH₂O	0	
 
 Compliance	60-79.99 ml/cmH₂O	1	
 
 Compliance	40-59.99 ml/cmH₂O	2	
 
 Compliance	30-39.99 ml/cmH₂O	3	
 
 Compliance	≤ 29.99 ml/cmH₂O	4	
  
 
* Abbreviations: $\text{Pao}_2/\text{Flo}_2$ = arterial oxygen tension to inspired oxygen concentration ratio; PEEP =: positive end-expiratory pressure.
 
The value of acute injury score is obtained by a mean of the items reported in the table above i.e., by dividing the aggregate sum by the number of components that were used (Protocol Section 14.4.5).
 
The acute injury score is computable only if 3 over 4 items (of the table above) are not missing.
 
The score will be classified as follows:
 
  
 	Score	
   
 No lung injury	0	
 
 Mild-to-moderate lung injury	0.1-2.5	
 
 Severe lung injury (ARDS)	>2.5	
  
 
Alveolar infiltrates are collected under "Chest Imaging" collected at "Screening day -1 or 1", "randomization and baseline assessments", at day 2, day 3, day 7, day 14
			Value	1. Chest X-ray (Number of quadrants with alveolar infiltrates)			0		0	1 quadrant		1	2 quadrants		2	3 quadrants		3	4 quadrants		4	2. Hypoxemia score ($\text{PaO}_2/\text{FiO}_2$ mmHg)			$\text{PaO}_2/\text{FiO}_2$	≥ 300	0	$\text{PaO}_2/\text{FiO}_2$	225-<300	1	$\text{PaO}_2/\text{FiO}_2$	175-<225	2	$\text{PaO}_2/\text{FiO}_2$	100-<175	3	$\text{PaO}_2/\text{FiO}_2$	<100	4	3. PEEP score (cmH ₂ O)			PEEP	≤ 5 cmH ₂ O	0	PEEP	6-8.99 cmH ₂ O	1	PEEP	9-11.99 cmH ₂ O	2	PEEP	12-14.99 cmH ₂ O	3	PEEP	≥ 15 cmH ₂ O	4	4. Compliance (ml/cmH ₂ O)			Compliance	≥ 80 ml/cmH ₂ O	0	Compliance	60-79.99 ml/cmH ₂ O	1	Compliance	40-59.99 ml/cmH ₂ O	2	Compliance	30-39.99 ml/cmH ₂ O	3	Compliance	≤ 29.99 ml/cmH ₂ O	4		Score	No lung injury	0	Mild-to-moderate lung injury	0.1-2.5	Severe lung injury (ARDS)	>2.5

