	
PaO₂/FiO₂ (mmHg) is collected under "Lung Function" at "Screening day -1 or 1", "randomization and baseline assessments", during the "daily assessment through extubation", during "assessments from extubation to hospital discharge (every 48h+/-8h)", at day 28 and at hospital discharge.
 
PEEP (cmH₂O) and Compliance (ml/cmH₂O) is collected under "Mechanical Ventilation Parameters" at "randomization and baseline assessments" and during the daily assessment through extubation. Mechanical Ventilation Parameters are collected at a specific date and time
 
Rules to match assessments for Acute Lung Injury score:
 
 1. keep date of Chest Imaging assessment from the i-th visit (namely, day 2,3,7,14) 2. link date of LF (Lung Function) and MV (Mechanical Ventilation) assessments with the date of CI (Chest Imaging), i.e., the assessments should be at the same date. 3. If no link is feasible Acute Lung Injury Score at that Visit will be missing. 
If chest imaging date is missing, please use study day based on date/time as follows:
 
Select the value of Lung Function assessment based on the study day rules considering date and time. Select the value Mechanical Ventilation assessment based on the study day rules considering date and time. If there is one measurement of LF and one measurement of MV falling in that specific study day (as defined by the rules considering date/time), select these values to compute the Acute Lung Injury score at that day. Do the same for each applicable post baseline day. (Example for day 7. Both LF and MV assessments should be collected in the window [First IMP Intake+132h, First IMP Intake+155h and 59min]). In case of more assessments at the same day, keep the assessment closer to the midpoint of the time interval. For instance: 2 assessments at day 7 [First IMP Intake Date/Time +132h, First IMP Intake Date/Time +155h and 59 min], the one closer to 144 hours from 1st IMP will be taken. If multiple records exist at the same distance from the midpoint of the time interval, select the first record collected in the eCRF.

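### Change in acute lung injury score can compare a four-item mean with a three-item mean, so a missing item alone moves an unchanged patient's score, in either direction

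*SAP*

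**What the plan says.** Protocol 14.4.5 defines four components, each scored 0 to 4, and sets a variable denominator: "The final score is obtained by dividing the collective score by the number of components that were used". SAP 11.1.1 (Table 3) repeats this ("by dividing the aggregate sum by the number of components that were used") and adds a minimum: "The acute injury score is computable only if 3 over 4 items (of the table above) are not missing". The chest component is "Chest X-ray (Number of quadrants with alveolar infiltrates)"; the others are hypoxaemia, PEEP and compliance. Scores above 2.5 are classed as severe.

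SAP 7.2.1.2 states: "Value and change from baseline in Acute lung injury score will be analyzed at Day 2, Day 3, Day 7, Day 14", for patients still intubated. It specifies a two-sample t-test, with a Mann-Whitney test if normality fails, and a class shift table. SAP 7.2.1 restricts tests of continuous secondary endpoints to the change from baseline. SAP 11.1.1 defines that change as the post-baseline value minus the baseline value.

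On matching, SAP 11.1.1 links lung function and ventilation data to the date of the film. If that fails, "If no link is feasible Acute Lung Injury Score at that Visit will be missing". There is a separate fallback: "If chest imaging date is missing, please use study day based on date/time as follows". It then selects lung function and ventilation values by study day.

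Protocol 6.1.3 schedules films at Days 2, 3, 7 and 14. For Germany, one of three participating countries, Protocol Appendix 14.5 says: "Chest imaging has to be performed as per local clinical practice/needs".

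**The concern.** A mean of available items is a reasonable value for one visit. A difference between two such means measures change only if both are built from the same items. The plan has no such condition and no check restricted to four-item scores. Followed exactly, it can record improvement or worsening in a patient whose measurements have not moved.

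The chest film is the obvious candidate for a missing item. Ventilation and lung function data are collected daily until extubation, whereas films are due at four follow-up visits only and follow local practice in Germany. The same problem arises if any other single item is missing.

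The change is the only quantity tested between arms for this endpoint, and the class shift table inherits the problem.

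**Working it through.** The plan states no figure for this point, so there is nothing to reproduce first.

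**Inputs.**
- Four items scored 0–4, mean of items used, at least three needed (SAP 11.1.1; Protocol 14.4.5).
- Class cut: severe if above 2.5 (SAP 11.1.1).
- Hypoxaemia item at least 2: entry requires PaO2/FiO2 of 200 or less (Protocol 4.1), and 175 to below 225 scores 2. This assumes that the baseline value still meets the entry limit.
- Chest item at least 2: entry requires bilateral opacities (Protocol 4.1). This assumes at least one quadrant on each side.

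**Formula.** Let x be the item missing at follow-up and m the mean of the other three, all unchanged since baseline.
- Baseline, four items: (x + 3m)/4
- Follow-up, three items: m
- Artefact: m − (x + 3m)/4 = (m − x)/4

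If the baseline lacks the item and the follow-up has it, the sign reverses.

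**Chest film missing at follow-up** (items in the order chest, hypoxaemia, PEEP, compliance):

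| Items | Four-item | Three-item | Artefact |
|---|---|---|---|
| 4, 3, 2, 3 | 3.00 | 2.67 | −0.33 |
| 4, 2, 2, 3 | 2.75 | 2.33 | −0.42 |
| 4, 2, 1, 3 | 2.50 | 2.00 | −0.50 |
| 4, 2, 0, 0 | 1.50 | 0.67 | −0.83 |
| 2, 3, 3, 3 | 2.75 | 3.00 | +0.25 |
| 2, 4, 4, 4 | 3.50 | 4.00 | +0.50 |

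The second row crosses from severe to mild-to-moderate. The reverse also occurs: items 2, 3, 3, 2 go from 2.50 to 2.67.

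**Enumeration.** The entry limits leave 3 × 3 × 5 × 5 = 225 item combinations.
- Range: −0.83 to +0.50. Without the entry limits (625 combinations) it is −1.00 to +1.00.
- False improvement in 149, false worsening in 54, no change in 22.
- Class changes in 25: 13 downward and 12 upward.

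These are counts of combinations, not of patients. The documents give no item distribution.

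**Another item missing.** For items 4, 3, 2, 3 without the PEEP item, the other three average 10/3 = 3.33, so the artefact is (3.33 − 2)/4 = +0.33.

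**Effect on an arm mean (illustration with assumed counts).** If 5 of 20 patients shift by −0.4, the arm's mean change moves by 5 × (−0.4)/20 = −0.1.

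**Same items at both times.** Both means are then identical for an unchanged patient, so the artefact is 0.

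**The case against.** Dividing by the components used is the protocol's own method, and the SAP tightens it by requiring three items. That stands for the value at a visit, but it does not settle how change should be formed.

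The fallback for a missing imaging date may be meant for a film recorded without a date, which would still supply a chest item. That is a fair reading. The point therefore rests on the three-item minimum, which permits the mismatch without the fallback.

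A reader might infer that a missing film makes patients look better, that improving patients skip films, and that the comparison is therefore biased between arms or by country. The documents do not support this chain:
- The direction depends on whether the chest item lies above or below the mean of the others, and nothing shows that it is usually the highest.
- Nothing says which patients miss films, or how many films German sites would omit.
- Patients well enough to be extubated are already outside this endpoint.
- Randomization is stratified by site (SAP 3.4.1.1) and the trial is double-blind, so local imaging practice should fall about equally on both arms.

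Finally, this is one of 16 secondary endpoints in SAP 3.5.2. The plan specifies no hypotheses (SAP 3.3), and neither primary endpoint is touched. That limits the weight of the point, but the defect remains.

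**Conclusion.** The point holds as a gap in the derivation rule. For an unchanged patient, a film present at baseline and missing at follow-up shifts the score by −0.83 to +0.50 within the entry limits, and the shift can change the severity class. The range rests on chest and hypoxaemia items of at least 2 at baseline; the formula itself needs no assumption beyond unchanged items.

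If missingness is unrelated to arm and outcome, the consequence is extra noise and a shift common to both arms. Between-arm bias would require missingness related to treatment or outcome, which is possible but undocumented. The correction is inexpensive and worth making before the analysis, in proportion to a secondary, descriptive endpoint.

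**What to change.** In SAP 11.1.1:
- Compute change from baseline, and both classes in the shift table, from the items present at both baseline and that visit, with at least three items in common; otherwise set change to missing.
- Keep the mean of available items for the by-visit value and class counts.
- Reword the minimum as at least 3 of 4 items.
- Report the number of three-item scores by arm and visit.

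The cost is a sentence or two in the SAP and a small programming change. The protocol's divide-by-components rule is kept, and a patient drops out of the change analysis only when fewer than three items are common. The drawback is that the baseline value or class used for change may differ between visits, so mean changes and shift-table totals will not always reconcile with the by-visit summaries. A table footnote should say so.
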